10.3.1 Other anti-tumor/cancer or study drugs

Other anti-tumor treatments not specified in the protocol are not permitted while subjects are receiving study treatment, including CDFA (NMPA)-approved Chinese herbal preparations for anti-tumor treatments (see [Appendix 9. Prohibited Traditional Chinese Medicines During the Study Period](#)) and immunomodulators (including but not limited to interferon, interleukin-2, and thymosin).

Participation in other drug/medical device clinical studies is not permitted.

Subjects can receive bisphosphonates for the treatment of bone metastases. If systemic treatment or local analgesia is not effective in controlling painful lesions of bone metastases, a small area of palliative radiotherapy (the area of the radiotherapy must be < 5% of the bone marrow region, and the percent bone marrow in human is shown in [Appendix 8. Percent Bone Marrow Content in Human Skeleton](#)) is allowed. Except for the above-mentioned treatments for bone metastases, other anti-tumor treatments such as chemotherapy, molecular targeted therapy, hormone therapy, immunotherapy, biological therapy, radiotherapy, and surgical treatment are not permitted.

10.3.2 Medications to be used with caution in subjects receiving apatinib

10.3.2.1 Drugs that may have interactions with apatinib mesylate

In vitro metabolic enzymes studies have shown that apatinib is mainly metabolized by CYP3A4. When apatinib is used concomitantly with strong inhibitors of CYP3A4 (itraconazole, clarithromycin, voriconazole, telithromycin, saquinavir, and ritonavir), the plasma concentration of apatinib may rise. When apatinib is used concomitantly with CYP3A4 inducers (dexamethasone, phenytoin, carbamazepine, rifampicin, phenobarbital, and rifapentine), the plasma concentration of apatinib may decrease. When other combined medications are needed, it is recommended to choose alternative drugs that do not inhibit or induce CYP3A4. If a strong inducer or inhibitor of CYP3A4 enzyme must be used concomitantly, it is necessary to consider whether to modify the dose based on clinical observation.

10.3.2.2 Drugs that prolong the QT interval of the heart

As tinib drugs may cause toxicities of prolonged QT interval in clinical applications, drugs that may prolong the QT interval should be used with caution during the study. These mainly include, but are not limited to, the following categories of drugs:

- ◆ Antibiotics: fluoroquinolones: sparfloxacin, gatifloxacin, levofloxacin, moxifloxacin, ofloxacin, ciprofloxacin; macrolides: erythromycin, clarithromycin, telithromycin, azithromycin, roxithromycin, and metronidazole.
- ◆ Antiarrhythmics: quinidine, procainamide, disopyramide, flecainide, propafenone, amiodarone, dronedarone, sotalol, dofetilide, and ibutilide.
- ◆ Drugs used to relieve angina: ranolazine and ivabradine.
- ◆ Antipsychotics: risperidone, fluphenazine, droperidol, haloperidol, thioridazine, pimozide, olanzapine, and clozapine.
- ◆ Antifungal drugs: voriconazole and posaconazole.
- ◆ Antimalarial drugs: mefloquine and chloroquine.
- ◆ Antihistamines: terfenadine, astemizole, and hydroxyzine.
- ◆ Gastrointestinal drugs: antiemetics: ondansetron, granisetron, dolasetron, droperidol (0.625-1.25 mg may be a safe dose), and hydroxyzine; prokinetics: cisapride, domperidone, and metoclopramide.
- ◆ Antidepressants: amitriptyline, imipramine, clomipramine, dosulepin, and doxepin.

10.3.3 Hematopoietic growth factor

According to the current edition of the "American Society of Clinical Oncology Clinical Practice Guideline", granulocyte colony stimulating factor is used as prophylaxis for neutropenia.

The probability that doxorubicin + ifosfamide causes febrile neutropenia is $\geq 20\%$, and it is recommended to use recombinant human granulocyte stimulating factor (such as mepagefilgrastim) for prophylaxis. Whether to continue to use recombinant human granulocyte stimulating factor (such as mepagefilgrastim) in the future depends on the outcome of previous use.

10.3.4 Dexrazoxane

Dexrazoxane is recommended when the cumulative dose of doxorubicin reaches 300 mg/m^2 , but is not recommended when the cumulative dose has not reached 300 mg/m^2 , so as not to affect the efficacy.

10.3.5 Mesna

The toxicity of acrolein, a degradation product of ifosfamide, to the urinary system is mainly hemorrhagic cystitis, while Mesna reacts with acrolein and becomes non-toxic products that are excreted in the urine, reducing the incidence of hemorrhagic cystitis. The recommended dose for single-dose injection of Mesna is 20% (w/w) of ifosfamide, injected at the start of ifosfamide infusion, at 4 h after the infusion, and at 8 h after the infusion (the total dose is 60%). The recommended infusion time is the scheduled time $\pm 10 \text{ min}$.

The recommended dose of ifosfamide in the protocol is 2 g/m^2 , and the recommended dose of mesna is 400 mg/m^2 per injection (the actual dose should not be less than the recommended dose).

10.3.6 Treatment for vomiting

Chemotherapy with anthracycline and ifosfamide may pose a risk of vomiting. The investigator shall determine the prophylactic drugs to be used.

The use of antiemetic drugs as a primary prevention method is not allowed for the investigational treatment group.

10.3.7 Anti-inflammatory treatment

Anti-inflammatory medications or narcotic analgesics can be given if there are no known or foreseeable drug interactions and if these drugs are not prohibited in the protocol.

10.3.8 Corticosteroids

Long-term, systemic use of corticosteroids for palliative or supportive treatment are prohibited. Emergency use, topical application, inhalation, eye drops, or local injections of corticosteroids are permitted.

10.3.9 Surgery

Any non-therapeutic tumor surgery conducted during the study period shall have its theoretical basis and necessity. The interval between the surgery and the treatment with study drug must not affect the recovery of the wound and the investigation on hemorrhage of unknown cause. An interruption of study treatment 1 week before the surgery is recommended. Re-initiation of study treatment after surgery will be determined on the basis of clinical assessment of wound healing and postoperative recovery.

10.4 Subject Compliance

Subjects in the investigational treatment group will be required to return or count all study drugs that have not been administered in the previous cycle before the start of the next cycle. The corresponding number of apatinib tablets will be documented and archived. The medication information in the subject's diary card will also be checked for consistency.

For SHR-1210, doxorubicin, and ifosfamide, the study center shall prepare the drugs complete the documentation as per the product brochure or package insert. The documentation system of the study center should include all relevant or required information with regards to preparation and administration.

11 STUDY PROCEDURES

Before the start of the study, subjects must read and sign the current version of ICF approved by the independent ethics committee/institutional review board (IEC/IRB). All the study procedures must be completed within the time window specified in the study schedule. The informed consent form shall be signed within 28 days before C1D1. Subjects who have failed previous screening may be screened again in this study. The informed consent form must be re-signed and a new subject number should be given for re-screening. If the re-screening fails, no further screening will be performed. Data from virology, echocardiography, and imaging assessment (tested at this study center only) performed prior to the signing of informed consent for clinical needs may be used if they are within the specified window period.

11.1 Screening

Unless otherwise stated, the following procedures must be completed within 28 days prior to the start of study treatment during at the screening visit (Day-28 to Day-1):

- Obtain informed consent form signed by the subject.
- Collecting demographics: gender, date of birth, ethnicity, etc.

- Tumor diagnosis: the location of the primary lesion, the date of pathological diagnosis, the pathological diagnosis (must be consistent with the term of the 2013 version of the WHO guidelines on soft tissue tumors), the time of progressive disease or recurrence, and the progressive disease (locally advanced, unresectable, or distantly metastatic).
- History of cancer treatment
 - ✓ History of tumor surgery: type, name, and date of surgery;
 - ✓ History of radiotherapy: site, total dose, and start and end dates;
 - ✓ History of neoadjuvant chemotherapy or chemotherapy: chemotherapy regimen, cycle, start and end dates, best response, reason for discontinuation of chemotherapy, whether recurrence happens within 6 months, and cumulative total dose of doxorubicin;
 - ✓ History of adjuvant chemotherapy: chemotherapy regimen, cycle, start and end dates, reason for discontinuation of chemotherapy, whether recurrence happens within 6 months, and cumulative total dose of doxorubicin;
- Medical history, surgical history, medication history (concomitant medications within 28 days before C1D1), history of drug or alcohol abuse, history of drug allergy, etc.;
- Virology: HBsAg (quantitative HBV DNA test if positive); HCV-Ab (quantitative HCV-RNA test if positive) and HIV-Ab: within 28 days before the first dose.
- Echocardiography: Including left ventricular ejection fraction (LVEF) assessment. Echocardiography will be performed once within 28 days prior to the first dose, and performed if clinically indicated thereafter.
- Imaging evaluation: CT or MRI of lesions in the head, chest, abdomen, pelvis, and other sites. Sites with bone metastasis as shown by bone scans, PET-CT, or clinical indications must also be reexamined by CT or MRI at baseline.
- Collection of adverse events: Collect adverse events starting from the signing of ICF.
- Concomitant medications/treatments: Concomitant medications/treatments within 28 days prior to the first dose of the study drug should be documented.

The following screening procedures should be completed within 7 days before the start of study treatment:

- ECOG PS.
- Vital signs: pulse, respiratory rate, temperature, and blood pressure.

- Comprehensive physical examination: height, weight, general condition, head and face, neck, chest, abdomen, perineum, extremities, etc.
- Hematology: Red blood cell count (RBC), hemoglobin (Hb), blood platelet count (PLT), white blood cell count (WBC), absolute neutrophil count (ANC), and lymphocyte count (LYM).
- Urinalysis: WBC, RBC, and urine protein. If urine protein is $\geq 2+$, then a quantitative 24-h urine protein test should be added.
- Fecal occult blood (OB): within 7 days before the first dose.
- Blood biochemistry: Alanine transaminase (ALT), aspartate aminotransferase (AST), gamma-glutamyl transferase (γ -GT), total bilirubin (TBIL), direct bilirubin (DBIL), alkaline phosphatase (AKP), blood urea nitrogen (BUN) or urea, total protein (TP), albumin (ALB), creatinine (Cr), blood glucose (GLU), serum potassium (K $^{+}$), serum sodium (Na $^{+}$), serum calcium (Ca $^{2+}$), serum magnesium (Mg $^{2+}$), and blood chloride (Cl $^{-}$).
- Coagulation function: Activated partial thromboplastin time (APTT), prothrombin time (PT), thrombin time (TT), fibrinogen (FIB), and international normalized ratio (INR).
- Thyroid function: Including serum thyroid stimulating hormone (TSH), free triiodothyronine (FT3), and free thyroxine (FT4). If FT3 and FT4 cannot be obtained, T3 and T4 are allowed for substitution;
- Myocardial zymogram: lactate dehydrogenase (LDH), creatine kinase (CK), and hybrid creatine kinase (CK-MB)
- 12-Lead ECG: Attention should be paid to heart rate, QT, QTcF, and PR intervals. The investigator may decide to add other investigations if the results are abnormal.
- Pregnancy test (serum pregnancy test will be performed for women of childbearing potential).
- Quality of life score.

11.2 Treatment Period

11.2.1 Treatment period for the investigational treatment group

The treatment period for the investigational treatment group will start from the first dose of the subject. The first dose of the study drugs should be given as close as possible to the time of completing the screening examinations and confirming the subjects' eligibility for the study. Each treatment cycle lasts for 21 days.

◆ **The following should be completed on C1D1:**

- Dispensation of study drugs in the investigational treatment group: Apatinib tablets are permitted to be dispensed on the day before or on the day of administration.
- Treatment with SHR-1210 and apatinib
- Pharmacokinetics and immunogenicity test for the investigational treatment group: Approximately 4-6 mL of peripheral venous blood will be collected within 0.5 h before the administration of SHR-1210 on C1D1 for pharmacokinetics/immunogenicity test of SHR-1210; Approximately 2-4 mL of peripheral venous blood will be collected within 0.5 h before and at 4 h (\pm 10 min) after the administration of apatinib on C1D1 for pharmacokinetics test of apatinib.
- Adverse event
- Recording of concomitant medications and concomitant treatments
- Dispensation and filling in of the subject diary card

◆ **The following should be completed on day 1 of each cycle from cycle 2 onwards:**

- ECOG PS
- Vital signs
- Physical examination
- Hematology
- Fecal occult blood
- Blood biochemistry
- 12-Lead ECG
- Dispensation and retrieval of study drugs of the investigational treatment group: Apatinib tablets are allowed to be dispensed at the scheduled time point within \pm 3 days; remaining apatinib must be retrieved before each dispensation. Unscheduled drug dispensation and retrieval are permitted.
- Pharmacokinetics/immunogenicity test: Within 0.5 h pre-administration on C2D1, C4D1, C6D1, C9D1 and every 4 cycles thereafter, with 4-6 mL of peripheral venous blood collected at each time point for pharmacokinetics/immunogenicity studies of SHR-1210; 4-6 mL of peripheral venous blood will be collected once 30 days after the last dose. Approximately 2-4 mL of peripheral venous blood will be collected within 0.5 h before and at 4 h (\pm 10 min) after the administration of apatinib on C2D1, C4D1, and C6D1 for pharmacokinetics study of apatinib.

- Collection of AEs
- Documentation of concomitant medications/concomitant treatments
- Dispensation and filling in of the subject diary card

◆ **The following should be completed on day 1 of every 2 cycles from cycle 3 onwards:**

- Urinalysis
- Coagulation function
- Thyroid function
- Blood pregnancy test
- Tumor imaging examination: Imaging examinations will be performed once every 2 cycles (6 weeks) in the first 16 treatment cycles of the study treatment period and once every 4 cycles (12 weeks) thereafter. Imaging conditions should be the same as those at baseline (including slice thickness and contrast agent). The time window for imaging examination is \pm 7 days. Additional imaging evaluations may be performed if PD is suspected (e.g., worsening of symptoms)
- Quality of life score

11.2.2 Treatment period for the control group

The treatment period will start from the first dose of the subject in the control group. The first dose of the study drugs should be given as close as possible to the time of completing the screening examinations and confirming the subjects' eligibility for the study. Each treatment cycle lasts for 21 days.

◆ **The following should be completed on C1D1:**

- Treatment with doxorubicin + ifosfamide or ifosfamide monotherapy
- Adverse event
- Recording of concomitant medications and concomitant treatments

◆ **The following should be completed on day 1 of each cycle from cycle 2 onwards (additional chemotherapy cycles may be administered if deemed beneficial by the investigator):**

- ECOG PS
- Vital signs
- Physical examination

- Hematology
- Urinalysis
- Fecal occult blood
- Blood biochemistry
- Coagulation function
- Myocardial zymogram
- 12-Lead ECG
- Echocardiography
- Blood pregnancy test: Once every 2 cycles from cycle 3 onwards
- Treatment with doxorubicin + ifosfamide or ifosfamide monotherapy
- Collection of AEs
- Documentation of concomitant medications/concomitant treatments
- Tumor imaging examination: Imaging examinations will be performed once every 2 cycles (6 weeks) in the first 16 treatment cycles of the study treatment period and once every 4 cycles (12 weeks) thereafter. Imaging conditions should be the same as those at baseline (including slice thickness and contrast agent). The time window for tumor evaluation is \pm 7 days. Additional tumor evaluations may be performed if PD is suspected (for example, worsening of symptoms).
- Quality of life score: Quality of life scoring will be performed once every 2 cycles in the first 16 treatment cycles from cycle 3 onwards and once every 4 cycles from cycle 17 onwards.

11.3 Follow-Up Period

11.3.1 Safety follow-up for the investigational treatment group

The safety follow-up for the combined medication of SHR-1210 and apatinib will start from the last dose of study treatment. Follow-ups will be performed once every 30 days (\pm 5 days) until 90 days after the last dose.

The first safety follow-up (30 \pm 5 days) will be carried out at the study center where the evaluations specified in the protocol are completed. The second (60 \pm 5 days) and the third (90 \pm 5 days) follow-up will be made via phone calls. The information on new anti-tumor treatment, survival, concomitant medications/concomitant treatments, and adverse events will be collected.

- ◆ At the first safety follow-up (30 ± 5 days), subjects should return to the study center to complete the following assessments:
 - ECOG PS
 - Vital signs
 - Physical examination
 - Hematology
 - Urinalysis
 - Fecal occult blood
 - Blood biochemistry
 - Thyroid function
 - Coagulation function
 - Myocardial zymogram
 - 12-Lead ECG
 - Imaging examination: Subjects who discontinue the study treatment for reasons other than radiographic progression will still be followed up according to the established cycle. If no imaging examination is performed within 4 weeks before the last dose, an imaging examination must be performed within 30 days after the last dose.
 - Pharmacokinetics and immunogenicity test: 4-6 mL of peripheral venous blood will be collected 30 days (± 5 days) after the last dose for pharmacokinetics and immunogenicity tests of SHR-1210.
 - Adverse events: Recorded from the date of signing the informed consent form to the end of the safety follow-up period. If a new anti-tumor treatment is initiated during this period, only treatment-related AEs will be collected after the start of the new anti-tumor treatment.
 - Concomitant medications/treatments
 - New anti-tumor treatment
 - Quality of life score
- ◆ For the second (60 days after the last dose) and the third safety follow-ups (90 days after the last dose), the subjects' subsequent anti-tumor treatment, survival, adverse events, and concomitant medications/treatments will be collected via phone interviews.

11.3.2 Safety follow-up for the control group

The safety follow-up period for the combined medication of doxorubicin and ifosfamide will start from 21 days (± 5 days) after the last dose.

- ◆ At the safety follow-up (21 ± 5 days), subjects should return to the study center to complete the following assessments:
 - ECOG PS
 - Vital signs
 - Physical examination
 - Hematology
 - Urinalysis
 - Fecal occult blood
 - Blood biochemistry
 - Thyroid function
 - Coagulation function
 - Myocardial zymogram
 - 12-Lead ECG
 - Echocardiography
 - Imaging examination: Subjects who discontinue the study treatment for reasons other than radiographic progression will still be followed up according to the established cycle if no imaging assessment is performed within 4 weeks before the last dose. An imaging examination must be performed within 21 days after the last dose.
 - Adverse events: Recorded from the date of signing the informed consent form to the end of the safety follow-up period. If a new anti-tumor treatment is initiated during this period, only treatment-related AEs will be collected after the start of the new anti-tumor treatment
 - Concomitant medication/treatments: Those within 28 days before the first dose of study medication to the new anti-tumor treatment will be documented; afterward, only concomitant medications for treatment-related AEs are documented.
 - New anti-tumor treatment
 - Quality of life score

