	D-28 to D-1	D-7 to D-1	D1	D1 (once every 1 cycle)	D1 (once every 2 cycles)	D1 (once every 4 cycles)	21 days after the last dose	Once every 2 months
Time Window				±3	±7	±7	±5	±5
Signing of Informed Consent Form ^[1]	×							
Demographics, Medical History, and Treatment History ^[2]	×							
Inclusion/Exclusion Criteria and Randomization		×	(Eligibility for randomization)					
ECOG PS ^[3]		×		×			×	
Vital Signs ^[4]		×		×			×	
Physical Examination ^[5]		×		×			×	
Virology ^[6]	×							
Hematology ^[7]		×		×			×	
Urinalysis ^[8]		×		×			×	
Fecal Occult Blood Test ^[9]		×		×			×	
Blood Biochemistry ^[10]		×		×			×	
Coagulation Function ^[11]		×		×			×	
Thyroid Function ^[12]		×					×	
Myocardial Zymogram ^[13]		×		×			×	
12-Lead ECG ^[14]		×		×			×	
Echocardiography ^[15]	×			×			×	
Pregnancy Test ^[16]		×		× (once every 2 cycles from cycle 3 onwards)			×	

STUDY PROCEDURES	Screening Period		Cycle 1	Cycles 2-6	Cycles 7-16	Cycle 17 and beyond	Safety Visit ^[22]	Survival Follow-Up ^[23]
	D-28 to D-1	D-7 to D-1	D1	D1 (once every 1 cycle)	D1 (once every 2 cycles)	D1 (once every 4 cycles)	21 days after the last dose	Once every 2 months
Tumor Imaging Examination ^[17]	×			×	(once every 2 cycles from cycle 3 onwards)	×	×	×
Study Treatment ^[18]			×	×				
Adverse Events ^[19]	×	×	×	×	×	×	×	
Concomitant Medications/ Treatments ^[20]	×	×	×	×	×	×	×	
Quality of Life Score ^[21]		×		×	(once every 2 cycles from cycle 3 onwards)	×	×	
Subsequent Anti-Tumor Treatment and Survival Status							×	×

Note: In addition to the examinations and time points listed in the table, the investigator may add visits and other examinations if needed. Subjects crossed over for SHR-1210 combined with apatinib will be followed up according to the crossover treatment flow chart.

- [1] Subjects who have failed previous screening may be screened again in this study. The informed consent form must be re-signed and a new subject number should be given for re-screening. If the re-screening fails, no further screening will be performed. Data from virology, echocardiography, and imaging assessment (tested at this study center only) performed prior to the signing of informed consent for clinical needs may be used if they are within the specified window period.

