- [17] Tumor imaging evaluation: CT or MRI of lesions in the head, chest, abdomen, pelvis, and other sites. Sites with bone metastasis as shown by bone scans, PET-CT, or clinical indications must also be reexamined by CT or MRI at baseline but no longer undergo bone scan or PET-CT for efficacy follow-up. CT or MRI follow-ups of lesions in the head, chest, abdomen, pelvis, and other sites will be performed at each response evaluation. The CT/MRI examination methods and techniques for a subject shall remain the same throughout the study period.
 - ✓ At screening, tumor evaluations (at this study center only) up to 4 weeks before the first dose and before signing the informed consent may be used as long as they meet the requirements.

- ✓ Study treatment period: The imaging examination cycles will start from C1D1. In the first 16 treatment cycles, imaging examinations will be performed once every 2 cycles (the first assessment will be on C3D1), and once every 4 cycles thereafter. Imaging examinations will no longer be performed in case of radiographic progression; subjects who discontinue the study treatment for reasons other than radiographic progression will still be followed up according to the established cycle. If the previous imaging examination does not show progression and no imaging examination is performed within 4 weeks before the 21-day visit after the last dose, an imaging examination must be performed at the 21-day visit after the last dose. The time window for tumor evaluation is \pm 7 days. Additional tumor evaluations may be performed if PD is suspected (for example, worsening of symptoms).
- [18] Study treatment: (doxorubicin + ifosfamide/ifosfamide monotherapy): doxorubicin 60 mg/m², on D1, ifosfamide 2 g/m²/d, on D1-D4, q3w, and 6 cycles are recommended; if the investigator considers that the subject benefits from the chemotherapy, additional chemotherapy cycles may be administered; the content of visits in subsequent treatment cycles will be the same as those in cycles 2-6. If intolerance is noted, the investigator may delay the administration of this cycle or the chemotherapy drug, and adjust the administration time of the next cycle to 21 days after the administration of the previous cycle. If the maximum cumulative dose of doxorubicin is reached, the treatment will be switched to ifosfamide monotherapy 2 g/m²/d on D1-D5 q3w.

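### Protocol 11.3.2 makes control-arm scanning after treatment conditional, contradicting the control schedule's own footnote [17] on imaging for the primary endpoint

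*Protocol*

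**What the plan says.** The Protocol states the rule for imaging after treatment stops in several places.

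- **11.3.2, control arm.** If treatment ends and imaging has not shown progression, subjects, in the section's words, "will still be followed up according to the established cycle if no imaging assessment is performed within 4 weeks before the last dose". A separate sentence follows: "An imaging examination must be performed within 21 days after the last dose".
- **11.3.1, investigational arm.** The continuation sentence ends before any condition. The condition, "If no imaging examination is performed within 4 weeks before the last dose", opens the next sentence and governs one scan only, due no later than 30 days from the final administration.
- **Control schedule (section 2), footnote [17].** "subjects who discontinue the study treatment for reasons other than radiographic progression will still be followed up according to the established cycle", with no condition. A scan at the safety visit is added if the previous scan shows no progression and "no imaging examination is performed within 4 weeks before the 21-day visit after the last dose". The investigational schedule's footnote [17] has the same structure, tied to its 30-day visit.
- **Control schedule table.** The imaging row carries the note "once every 2 cycles from cycle 3 onwards" and is also marked for Cycles 7-16 and for Cycle 17 and beyond, where the study-treatment row is blank.

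SAP 4.1.1.1 censors a subject without progression or death at the last tumor evaluation.

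**The concern.** The primary endpoint is IRC-assessed PFS, so both arms need the same scanning rule until progression. Of the texts above, 11.3.2 alone attaches the 4-week condition to continued scanning rather than to one extra scan, and it does so for the arm in which stopping without progression is built in, because six cycles are recommended. The rest of section 11 does not correct it: 11.2.2 sets the scan schedule within the treatment period, and survival follow-up in 11.3.3 is by telephone or similar and lists no imaging.

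A site working from 11.3.2 could therefore stop scanning a progression-free control subject. Under the SAP this becomes early censoring in one arm of an open-label trial. The Protocol's RECIST appendix (4.5) asks for calendar-based assessment in randomized studies so that timing does not become unbalanced between groups. Crossover under 8.3.4 also depends on progression being found during or after chemotherapy.

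**Working it through.** **1. Does an on-schedule subject fail the condition?** Inputs: 21-day cycles (11.2.2); scans at C3D1 and every 2 cycles, ±7 days, and ifosfamide on D1-D4 with six cycles recommended (control schedule footnotes [17] and [18]). With C1D1 as day 1, cycle k starts on day 1 + 21(k − 1).

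- C5D1 scan: 1 + 84 = day 85. C7D1 scan: 1 + 126 = day 127.
- Last dose, C6D4: 1 + 105 + 3 = day 109.
- Gap: 109 − 85 = 24 days, under 28. With the ±7-day window it is 17 to 31 days, so the condition is met only if the scan was 5 to 7 days early or dosing was delayed.
- For any on-schedule stop on D4 of cycle 3 or later, within the first 16 cycles, the gap is 3 days (odd cycle) or 24 days (even cycle). The condition fails in the ordinary case, not only at six cycles.

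**2. What each text then requires.**

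- 11.3.2 literally: one scan by 109 + 21 = day 130, then no routine scanning.
- Footnote [17]: from day 85 to the 21-day visit is 130 − 85 = 45 days, so if there has been no later scan the extra scan is triggered. Routine scanning continues.
- The two 4-week reference points (last dose, 24 days; visit, 45 days) fall on opposite sides of the threshold.

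**3. The plan's own figures.** Inputs: medians 4.5 and 7.0 months, HR 0.64, 20 months' accrual, 26 months in total, one-sided 0.025, 90% power. Lan-DeMets O'Brien-Fleming spending at 143 and 214 events gives boundaries of −2.506 and −1.993 and power of 90.1%, matching the plan. For exponential PFS with rate λ = ln 2/median, the expected event fraction is 1 − [exp(−6λ) − exp(−26λ)]/(20λ).

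- Control: 0.877 × 131 = 114.9. Investigational: 0.760 × 131 = 99.5.
- Total 214.4 from 262 subjects, matching 214. 262/0.9 gives 292.

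**4. Upper bound for the literal reading.** Assume every control subject stops at six cycles, is censored at day 130 (130/30.4375 = 4.27 months, taking C1D1 as randomization), and contributes no later event of any kind.

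- Control PFS at day 130: exp(−0.154 × 4.27) = 0.518, so the control median might not be estimable.
- Control events: 131 × 0.482 = 63.1. Total: 63.1 + 99.5 = 162.7, about 163. With 292 subjects the total falls from 239 to 181.
- Power in 4,000 simulated trials of 262 subjects (no dropout, final boundary −1.993 at month 26, no interim look): 88% with full follow-up, 62% with the censoring.
- Analytic check: after day 130 no control subject is at risk, so only earlier events inform the log-rank test. Investigational events by then are 131 × (1 − exp(−0.0990 × 4.27)) = 45.2, and 63.1 + 45.2 = 108. With HR 4.5/7 = 0.643, the expected z is 0.442 × √108/2 = 2.30, and Φ(2.30 − 1.993) = 0.62.

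**5. A partial case.** If half the control subjects were affected, eventual events among 262 subjects could still reach 65.5 × 0.482 + 65.5 + 131 = 228, before dropout. That exceeds 214.

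**The case against.** The strongest reply is that continued control scanning is already required. Footnote [17] belongs to the control schedule and says so without condition, the table marks imaging beyond the treatment columns, and 8.3.4 expects progression to be found after chemotherapy. Moving one full stop in 11.3.2 gives the structure of 11.3.1, and the literal rule is odd, since it would keep on schedule those without a recent scan and drop those with one. It also says *if*, not *only if*. All of this stands. A reader might infer that the protocol as a whole ends PFS imaging for control subjects who finish six cycles; the documents do not support that.

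Nor do they support the inference that the control arm gains an extra assessment time. For the six-cycle subject, the scan due by day 130 falls within the window of the scheduled day-127 scan, and the investigational arm has its own end-of-treatment scan. The mismatch between last dose and visit occurs in both arms and affects only that one scan.

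On size, extra cycles are allowed, deaths are PFS events, scans are permitted when progression is suspected, and the final analysis waits for 214 events. With partial adherence to 11.3.2, the event trigger would turn part of the loss into delay. Deaths help less than they seem to: the SAP censors a subject who missed two or more consecutive scheduled assessments before death, and whether these scans count as scheduled depends on which text governs.

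What does not stand is that the sentence is harmless. It is in the control arm's procedures text, and nothing says which text prevails.

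**Conclusion.** The point holds as an internal contradiction on primary-endpoint imaging. Section 11.3.2 as printed conflicts with the control footnote and table and departs from the rule for the other arm. An on-schedule six-cycle subject fails its condition (24 days against 28), so a site that follows it literally could stop scanning after about day 130, with censoring there in the control arm only.

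The documents do not fix the size, because it depends on how many sites follow 11.3.2 over footnote [17]. The fall to about 163 events and 62% power at month 26 needs all control subjects to stop at six cycles, all later control events to be lost, and analysis at that time. It is an extreme upper bound, and a reader should not take it as the expected loss. If sites follow footnote [17], the design figures are unaffected.

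**What to change.** - Rewrite 11.3.2 to agree with footnote [17] and 11.3.1: scanning on the established schedule until radiographic progression, without condition, in both arms.
- State that this includes subjects who complete planned chemotherapy. The present texts refer only to subjects who discontinue, which may not be read as covering completion.
- Let the 4-week condition govern only the extra end-of-treatment scan.
- Use one reference point for the 4 weeks, last dose or visit, in 11.3.1, 11.3.2 and the schedule footnotes.

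The cost is a protocol wording change. The planned schedule, event target and sample size stay as they are.
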